4.2 Protocol Deviations

A protocol deviation is any change, divergence, or departure from the study design or procedures defined in the clinical protocol. Protocol deviations will be classified by the sponsor or designee prior to primary analysis and important protocol deviations will be identified as those deviations from the study protocol that may significantly impact the completeness, accuracy, and/or reliability of the trial data; or that may significantly affect a subject's rights, safety, or well-being (ICH E3 R1 Guidelines 2013). Number and percentage of subjects with important protocol deviation will be summarised.

Protocol deviations will be listed.

4.3 Demography and Baseline Characteristics

Descriptive statistics, including number of subjects (n), mean, STD, median, minimum and maximum, will be used to summarize the following parameters:

- Age (years)
- Weight (kg) at Baseline
- Height (cm) at Baseline
- Body Mass Index (kg/m²) at Baseline

The following demographic categories will be summarized with the number and percentage of subjects:

- Age Group (years): < 65, ≥ 65 to < 75, ≥ 75
- Gender: Male, Female, Undifferentiated, and Unknown
- Ethnicity: Hispanic or Latino, Not Hispanic or Latino, Not Reported, Unknown, and Other. The details of other ethnicities will be listed as appropriate.
- Race: American Indian or Alaska Native, Asian, Black or African American, Native Hawaiian or Other Pacific Islander, White, Other, Not Reported, and Unknown. The details of other races will be listed as appropriate.

4.4 Disease History

The following disease history will be summarized with descriptive statistics (n, mean, STD, median, minimum and maximum) using safety analysis set:

- Time since initial diagnosis (Months) = (Date of first NT-I7 Dose - Date of initial Diagnosis)/30.4375
- Time since histopathologic diagnosis (Months) = (Date of first NT-I7 Dose - Date of histopathologic diagnosis)/30.4375

The following disease history categories will be summarized with the number and percentage of subjects:

- Type of cancer diagnosed (TNBC, NSCLC, SCLC, CRC (left side, right side, both side), PC, OC)
- Stage at diagnosis (1, 2, 3, 4)
- Substage at diagnosis (Alpha) (A, B, C, E, X, Bulky)
- Substage at enrollment (Alpha) (A, B, C, E, X, Bulky)
- T staging at enrollment (T0, T1, T2, T3, T4)
- N staging at enrollment (N0, N1, N2, N3)
- M staging at enrollment (M0, M1)
- Histopathology performed on primary tumor and metastatic site
- Eastern Cooperative Oncology Group (ECOG) Status at Baseline (0 or 1)

Baseline PD-L1 IHC expression and Immunohistochemical analysis results for available data in the arm performed will be listed.

In addition, below baseline characteristics (descriptive statistics for continuous variable or number/percentage for categorical variable) will be provided based on data as appropriate

- Liver metastasis at baseline (Yes)
- Subjects with liver metastasis at baseline: 0, 1, ≥ 2
- Sum of target lesions at baseline (mm): ≤ 100 mm, > 100 mm
- Absolute lymphocyte count (ALC): $\leq 10^3/\mu\text{L}$, $> 10^3/\mu\text{L}$

4.5 Prior Systemic Anti-Cancer Therapy

Regimen Number will be summarized with descriptive statistics (n, mean, STD, median, minimum and maximum) using safety analysis set.

The following prior systemic anti-cancer therapy categories will be summarized with the number and percentage of subjects:

- Type of therapy (chemotherapy, hormonal therapy, biologic therapy, targeted therapy, other)
- Regimen number (1, 2, 3, ≥ 4)
- Therapy setting (adjuvant, conditioning, consolidation, induction, locally advanced, maintenance, metastatic, mobilization, neo-adjuvant, preventative, salvage)
- Best response at last regimen (CR, PR, SD, PD, Not Evaluable [NE], Unknown)
- Number of prior anti-cancer therapy: 0, 1, 2, 3, 4, ≥ 5 . Therapy setting of 'adjuvant', 'neo-adjuvant', 'maintenance' will be excluded from the number of prior anti-cancer therapy.

4.6 Medical History

System organ class (SOC) and preferred term (PT) of medical history will be coded with MedDRA 27.1. A subject will be counted only once within one PT if the subject reported

the same PT multiple times. The summary will be sorted by the frequency of SOCs and PTs in overall total.

Medical history information collected on “Medical History” case report form (CRF) page will be listed.

4.7 Prior and Concomitant Medications

All medications will be coded using the WHO-Drug Dictionary September 2024 B3.

Prior medications are all medications (prescription and over-the-counter [OTC]) taken within 30 days of Screening visit. Concomitant medications are all medications (prescription and OTC) taken between 7 days prior to Cycle 1, Day 1 through the Safety Follow-up visit (up to 30 days after the last dose of study treatment).

Prior and concomitant medications will be summarized by anatomical therapeutic classification (ATC) class (2nd level, chemical subgroup) and preferred name. A subject will only be counted once within each ATC-2 code and within each preferred name.

Prior and concomitant medications will also be presented in data listings.

4.8 Exposure of NT-I7 and Pembrolizumab

Exposure for NT-I7 and pembrolizumab will be summarized separately using safety analysis set by DL or arm depending on the study phase presented.

The exposure summary of NT-I7 and Pembrolizumab will be presented (descriptive statistics for continuous variables and number of subjects/percentages for categorical variables) for the following:

- Number of doses received
- NT-I7 treatment duration (weeks) = (date of last dose – date of first dose + 43)/7.
- Pembrolizumab Treatment duration (weeks) = (date of last dose – date of first dose + 22)/7.
- Cumulative Dose (mg) = Sum (actual dose per administration (mg))
- Average Dose per Cycle (mg/cycle) = Sum (actual dose per administration (mg))/number of treatment cycle started
- NT-I7 average actual dose per administration (ug/kg) = Sum (actual dose per administration (mg)*1000/weight)/number of doses received
- Pembrolizumab average actual dose per administration (mg) = Sum (actual dose per administration (mg)/number of doses received
- NT-I7 Treatment compliance (%) = (Sum (total dose administered (mg))/Sum (dose per administration planned(ug/kg)*weight (kg)/1000)) *100
- Pembrolizumab Treatment compliance (%) = (Sum (total dose administered (mg))/sum (dose per administration planned(mg)))*100
- Number of subjects with at least one dose not administered with a breakdown of reasons for dose not taken

- Number of subjects with at least one dose adjustment with a breakdown of reasons for dose adjustment.
- Number of subjects with at least one infusion interruption with a breakdown of reasons for infusion interruption (Pembrolizumab only).

All study drug exposure data will be listed.

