**Table 2: Study treatment details**

Study Treatment	Dosage Formulation	Unit Dose Strength	Dosage Level(s)	Route	Regimen or Treatment Period	Sourcing
NT-I7	Solution for injection	25 mg/mL	Dose in $\mu\text{g}/\text{kg}^a$ Q6W	IM injection	Day 1 of alternate cycle	Provided centrally by Sponsor
Pembrolizumab (MK-3475)	Solution for infusion	100 mg/vial	200 mg Q3W	IV infusion	Day 1 of every cycle	Provided centrally by Sponsor

Abbreviations: IM=intramuscular; IV=intravenous.

aRefer to Sections 5.4, 5.5 and 5.6 for assigned dose level.

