The Biomarker Cohort will enroll up to 10 evaluable subjects with CPI naïve R/R OC. The starting dose level of NT-I7 is planned at 960 µg/kg IM Q6W to further evaluate the tolerability of the starting regimen. Pembrolizumab dose is fixed at 200 mg IV Q3W. Subjects who tolerate at least 4 cycles of treatment without Grade ≥ 3 AEs and all Grade 2 AEs have resolved to Grade ≤ 1 , the dose may be escalated to NT-I7 1200 µg/kg IM Q6W at Cycle 5. This cohort will test intra-patient dose escalation and collect samples for biomarker analyses at 2 different dosages.

One treatment cycle is defined as 21 days (3 weeks) with NT-I7 administered intramuscularly (IM) once every 6 weeks (Q6W), and pembrolizumab administered intravenously (IV) once every 3 weeks (Q3W).

On days where both drugs are given, pembrolizumab will be given prior to NT-I7. Treatment completion is defined as completion of 35 cycles of administration (approximately 2 years) with pembrolizumab and NT-I7.

Figure 1 Study Design

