2.3 Study Day

Study Day is relative to the first dose date of study drugs:

- If analysis date is on/after the date of first dose of study drugs, Study Day = analysis date – treatment start date +1.
- If analysis date is before the date of first dose of study drugs, Study Day = analysis date – treatment start date.

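### Both treatment-duration formulas in SAP 4.8 count one day too many and set no limit at death or data cut-off

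*SAP*

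**What the plan says.** SAP 4.8 defines two durations in weeks, each starting from the last dose date minus the first. NT-I7 uses "date of first dose + 43)/7" and pembrolizumab uses "date of first dose + 22)/7". Both are summarised on the safety analysis set by dose level or arm, and SAP 5 lists the exposure summary among the interim outputs. No rule in SAP 4.8 ends either duration at death, data cut-off or end of study.

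SAP 1.3.1 sets the schedule: "One treatment cycle is defined as 21 days (3 weeks) with NT-I7 administered intramuscularly (IM) once every 6 weeks (Q6W"), and "Pembrolizumab dose is fixed at 200 mg IV Q3W". Protocol Table 2 places NT-I7 on "Day 1 of alternate cycle". Treatment is complete at "completion of 35 cycles of administration (approximately 2 years"). SAP 2.3 counts days inclusively: "Study Day = analysis date – treatment start date +1".

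**The concern.** The constants are 43 and 22, but the intervals are 42 and 21 days. Crediting one dosing interval after the last dose is a recognised convention, and a full interval already includes the dosing day. It appears that the inclusive +1 was then added a second time.

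The formulas also treat every subject as exposed for a whole interval after the last dose, including a subject who dies within days of it. Elsewhere the SAP does respect such limits: Tables 1 and 2 in SAP 2.8 stop imputed adverse-event and medication end dates at death or data cut-off. At stake is the accuracy of a duration reported for every dose level and arm. The population has relapsed or refractory advanced disease, where death within six weeks of an NT-I7 dose is foreseeable.

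**Working it through.** **Inputs**
- Constants: 43 (NT-I7) and 22 (pembrolizumab), SAP 4.8.
- Intervals: 6 × 7 = 42 days and 3 × 7 = 21 days, SAP 1.3.1. SAP 4.14.1 agrees: it puts the Cycle 2 Day 1 pre-dose sample at 504 h (504/24 = 21 days) and the Cycle 3 Day 1 pre-dose sample at 1008 h (1008/24 = 42 days) after Cycle 1 Day 1.
- Full course: 35 cycles. With NT-I7 on odd cycles, the last possible dose of either drug on schedule is Cycle 35 Day 1, which is 34 × 21 = 714 days after the first.

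**Step 1. Where the constants come from.** 43 = 42 + 1 and 22 = 21 + 1, so each is a full interval plus an inclusive day. A dose on Day 1 covers Days 1-42 (or 1-21), and the next dose falls on Day 43 (or 22). The formulas therefore count the next dosing day as well.

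**Step 2. Size of the extra day.**

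| Case | SAP 4.8 | Interval only | Excess |
|---|---|---|---|
| One NT-I7 dose | 43/7 = 6.14 wk | 42/7 = 6.00 wk | 1/42 = 2.4% |
| One pembrolizumab dose | 22/7 = 3.14 wk | 21/7 = 3.00 wk | 1/21 = 4.8% |
| NT-I7, 35 cycles on schedule | (714+43)/7 = 108.14 wk | (714+42)/7 = 108.00 wk | 1/756 = 0.13% |
| Pembrolizumab, 35 cycles on schedule | (714+22)/7 = 105.14 wk | (714+21)/7 = 105.00 wk | 1/735 = 0.14% |

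The absolute excess is always 1 day (1/7 = 0.14 week).

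**Step 3. Effect of having no limit.** Suppose death or cut-off falls d days after the last dose. The time lived or observed from that dose, counted inclusively, is d + 1 days. The SAP credits 43 or 22 days.
- NT-I7 excess = 43 - (d + 1) = 42 - d days, for d = 0 to 41.
- Pembrolizumab excess = 22 - (d + 1) = 21 - d days, for d = 0 to 20.
- For larger d there is no excess over time lived or observed.

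| d | NT-I7 excess (days) | Pembrolizumab excess (days) |
|---|---|---|
| 0 | 42 | 21 |
| 7 | 35 | 14 |
| 14 | 28 | 7 |
| 28 | 14 | 0 |
| 41 | 1 | 0 |

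As an illustration, take a subject who dies on Day 15 after one dose of NT-I7 (d = 14). The credited duration is 43/7 = 6.14 weeks, against 15/7 = 2.14 weeks lived.

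**Step 4. Would correcting the constants be enough?** No. With 42 and 21 but no limit, the largest excess falls only from 42 to 41 days for NT-I7 and from 21 to 20 for pembrolizumab.

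**Step 5. What uses these durations.** In SAP 4.8, dose counts, cumulative dose, average dose and compliance are built from doses, not from these constants. SAP 4.11.2 reports adverse events as frequencies and percentages of subjects, and its treatment-emergent window runs from the last dose date. No efficacy test, sample size or power figure uses duration. SAP 4.9.4.1 plans a swimmer plot of treatment duration but does not say whether it uses this variable.

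**The case against.** The strongest reply is that this is a convention for a descriptive variable, that one day is trivial over a full course, and that no passage states a duration that SAP 4.8 contradicts. The smallness of the single day stands. The reply does not rescue the constants: crediting an interval gives 42 and 21, crediting none gives 1, and 43 and 22 match neither.

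Several stronger readings are tempting, and the documents do not support them.
- *That reported exposure is impossible in general.* For a subject followed past the interval, one extra day does not make the value impossible. The duration exceeds time lived or observed only when death or cut-off comes within 42 (NT-I7) or 21 (pembrolizumab) days of the last dose.
- *That 105 weeks is a ceiling which 105.14 breaks.* Protocol 7.4 allows ±3 days at Day 1 visits from Cycle 2, Protocol 8.2.2 allows pembrolizumab interruptions, and Protocol 6.4.1 describes the two-year duration as approximate. Even the corrected interval rule gives NT-I7 108.00 weeks when the last dose is at Cycle 35.
- *That early progression inflates duration.* Under either formula, a subject who stops for progression and lives on is credited a full interval. The correction changes that duration by one day only.
- *That safety rates are biased through their denominator.* The SAP plans no exposure-adjusted adverse-event rates.

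The cut-off part is also limited. The final analysis follows database lock (SAP 2.9.2), and the active study ends with the last subject's 90-day safety visit (Protocol 6.6), which is longer than either interval. A cut-off limit would therefore bind mainly in interim outputs. The life-expectancy criterion of at least 12 weeks (Protocol 4.1) makes very early death less expected, but it does not exclude death soon after a later dose.

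**Conclusion.** The point holds as a minor but definite formula error. Followed as written, SAP 4.8 overstates every treatment duration by one day. It also credits time after death or cut-off: up to 42 days for NT-I7 and up to 21 for pembrolizumab, the extra day included. The missing limit is the larger part.

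This rests on two assumptions: that the intended convention credits one dosing interval after the last dose, as the constants imply, and that days are counted inclusively, as in SAP 2.3. The effect on any arm's summary cannot be computed, because the documents do not give the number of subjects who die or are cut off within an interval of the last dose. The consequence is confined to descriptive exposure summaries and, if it draws on this variable, the swimmer plot.

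**What to change.** Replace the two lines in SAP 4.8 with:
- NT-I7 duration (weeks) = (min[last dose + 41, death, data cut-off] - first dose + 1)/7
- Pembrolizumab duration (weeks) = (min[last dose + 20, death, data cut-off] - first dose + 1)/7

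Check: one dose with longer follow-up gives (41+1)/7 = 6.00 and (20+1)/7 = 3.00 weeks. Thirty-five pembrolizumab cycles on schedule give (714+20+1)/7 = 105.00 weeks. The Day 15 death gives 15/7 = 2.14 weeks for either drug.

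State in SAP 4.9.4.1 whether the swimmer plot uses these durations. If the sponsor prefers the present convention, SAP 4.8 should say so and give the reason.

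The cost is two formula lines in the SAP and the matching change in the exposure program. Reported durations become slightly shorter.

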#### 6.1.2. Pembrolizumab

Pembrolizumab will be administered using IV infusion on Day 1 of each 3-week treatment cycle after all procedures and assessments have been completed. [*NT-I7 to be administered 30-60 minutes post administration of pembrolizumab on days where concurrent administration is planned*].

Pembrolizumab will be administered as a dose of 200 mg using a 30-minute IV infusion. Sites should make every effort to target infusion timing to be as close to 30 minutes as possible. However, given the variability of infusion pumps from site to site, a window between -5 minutes and +10 minutes is permitted (i.e., infusion time is 30 minutes (-5 min/+10 min)).

On the even-numbered cycles (only pembrolizumab administered), vital signs need to be obtained within 60 minutes prior to the start of the pembrolizumab infusion.

*The Pembrolizumab Pharmacy Manual contains specific instructions for the preparation of the pembrolizumab infusion and administration of infusion solution.*

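### SAP 4.8 divides NT-I7 dose by every 3-week cycle started, though NT-I7 is scheduled only in odd cycles, so the average dose per cycle partly reflects the stopping cycle

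*SAP*

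**What the plan says.** SAP 4.8 lists the exposure measures for both drugs and states: "Exposure for NT-I7 and pembrolizumab will be summarized separately using safety analysis set by DL or arm". Treatment duration, dose per administration and compliance each have a separate formula for each drug. Dose per cycle has only one: "Average Dose per Cycle (mg/cycle) = Sum (actual dose per administration (mg))/number of treatment cycle started".

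The SAP's only definition of a cycle is in Section 1.3.1: "One treatment cycle is defined as 21 days (3 weeks) with NT-I7 administered intramuscularly (IM) once every 6 weeks (Q6W". Protocol Table 2 puts NT-I7 on "Day 1 of alternate cycle", and the Schedule of Assessments (Protocol 7.4) gives NT-I7 in odd cycles. Protocol 6.1.2 confirms the other half of the pattern: "On the even-numbered cycles (only pembrolizumab administered". Treatment completion is "completion of 35 cycles of administration (approximately 2 years".

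Elsewhere in SAP 4.8 the six-week interval is respected. The duration formula credits NT-I7 with six weeks after the last dose: "NT-I7 treatment duration (weeks) = (date of last dose – date of first dose + 43)/7".

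**The concern.** For pembrolizumab, the number of cycles started equals the number of scheduled doses, so the ratio is meaningful. For NT-I7 it is not. A subject who stops in an odd cycle is credited with a whole six-week dose set against a final interval that is only half counted. A subject who stops after an even cycle is not. Two subjects on the same dose with perfect adherence therefore get different values, and a subject who leaves in cycle 1 gets the highest of all.

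The table is presented by dose level in Phase 1b and by arm in Phase 2a, and SAP Section 5 also lists it for the interim analyses. NT-I7 is the drug whose dose was escalated. An arm with more cycle-1 stoppers will appear more heavily dosed on this row. The row is also in mg although NT-I7 is dosed by weight, so it carries body-weight differences as well.

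**Working it through.** The documents give no numerical value for this measure, so there is no figure to reproduce. The check applies the SAP formula to the documents' own schedule.

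**Inputs.** Cycle of 21 days (SAP 1.3.1); NT-I7 in odd cycles (Protocol Table 2 and 7.4); pembrolizumab 200 mg in every cycle; maximum 35 cycles; NT-I7 dose levels 480, 960 and 1200 µg/kg. Body weight of 70 kg is an assumption, used only for the mg column; the ratios do not depend on it.

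**Formula.** After k cycles started, with no dose missed or changed, the number of NT-I7 doses is ceil(k/2). With D the dose per administration, SAP average dose per cycle = D × ceil(k/2)/k.

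**Results at 1200 µg/kg** (70 kg × 1.2 mg/kg = 84 mg per dose):

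| k | NT-I7 doses | Ratio to D | µg/kg per cycle | mg per cycle |
|---|---|---|---|---|
| 1 | 1 | 1.00 | 1200 | 84.0 |
| 2 | 1 | 0.50 | 600 | 42.0 |
| 3 | 2 | 0.667 | 800 | 56.0 |
| 4 | 2 | 0.50 | 600 | 42.0 |
| 5 | 3 | 0.60 | 720 | 50.4 |
| 6 | 3 | 0.50 | 600 | 42.0 |
| 7 | 4 | 0.571 | 686 | 48.0 |
| 35 | 18 | 0.514 | 617 | 43.2 |

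**Spread.** Over k = 1 to 35: 1.00/0.50 = 2.00. From k = 3: 0.667/0.50 = 1.33. From k = 5: 0.60/0.50 = 1.20.

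**Contrast drug.** Pembrolizumab: 200k/k = 200 mg per cycle at every k.

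**Dose order.** A 960 µg/kg subject who stops in cycle 1 scores 960 per cycle. A 1200 µg/kg subject who stops after cycle 2 scores 1200/2 = 600. The order of the two dose levels is reversed with nothing missed.

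**First scan.** The first on-study scan is due at 6 weeks (SAP 4.9.1), which is about the start of cycle 3. Stopping just before or just after that dose gives 0.50 or 0.667. The lower value is 25% below the higher; a true step from 1200 to 960 is a 20% fall.

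**Group means.** As an illustration, suppose a proportion p of an arm stops in cycle 1 and the rest stop after an even cycle. The arm mean is D × (0.5 + 0.5p). A difference of 10 percentage points in p between arms then moves the means apart by 0.05D.

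**Does the numerator still respond?** Yes. Over five cycles, 1200 then 960 then 480 gives 2640/5 = 528 µg/kg per cycle, against 3600/5 = 720 with no reduction.

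**After the change.** Dividing by odd cycles started, ceil(k/2), returns D at every k from 1 to 35 for a fully dosed subject. The reduction sequence above gives 2640/3 = 880. If one of three scheduled doses of 1200 is omitted, the result is 2400/3 = 800.

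**The case against.** Four points can be made against this.

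*The row computes what its label says.* At even k, half a dose per 21-day cycle is the correct average for a six-weekly drug. This stands: the artefact is the end effect at odd k, and the 0.50 at even k is not under-reporting. No stated figure is wrong; the fault is one of definition.

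*Neighbouring rows carry the information.* SAP 4.8 also reports number of doses, cumulative dose, compliance, doses not given and dose adjustments with reasons, and a weight-based measure: "NT-I7 average actual dose per administration (ug/kg) = Sum (actual dose per administration (mg)*1000/weight)/number of doses received". This largely stands. That last row separates 1200 from 960, and cumulative dose shows that early stoppers received less. It does not make the per-cycle row harmless. Dose per administration divides by doses received, so it cannot show an omitted dose. Compliance divides by planned dose, but the SAP does not say whether an omitted administration stays in the planned sum.

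*A cycle could be read as an NT-I7 dosing cycle.* That would remove the problem, but the SAP does not say so and defines a cycle only as 21 days.

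*The numbers can be over-read.* A reader might infer that the row varies with stopping time and not with dose received. The documents do not support that, since the numerator falls with every reduction or missed dose. A reader might also take the 2-fold range as typical; it requires comparing a cycle-1 stopper with someone who stopped after an even cycle.

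**Conclusion.** The point holds as a defect in one descriptive row. With constant dosing and nothing missed, the NT-I7 average dose per cycle depends on the cycle in which the subject stops: up to 2-fold if cycle-1 stoppers are included, at most 1.33-fold from k = 3, at most 1.20-fold from k = 5. This rests on the 21-day cycle definition and the odd-cycle schedule, and on no assumption about weight. How far dose levels or arms are distorted depends on their mix of stopping cycles, which the documents do not give.

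If NT-I7 stops and pembrolizumab continues alone, which Protocol 8.2 allows with sponsor agreement, the value can fall below half a dose. That fall reflects NT-I7 not given and is not part of the artefact.

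A reader might go further and conclude that the Phase 1b assessment of dose level against safety and efficacy, or the Phase 2a decisions, are compromised. The documents do not support this. Results are grouped by dose level or arm, Go/No-Go rests on iRECIST response, and no hypothesis test uses this row.

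**What to change.** In SAP 4.8, split the row by drug as is already done for duration, dose per administration and compliance.

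- **NT-I7:** total actual dose in µg/kg divided by the number of 6-week NT-I7 dosing intervals (odd-numbered cycles) started. Scheduled but omitted administrations count in the denominator. Report in µg/kg per interval. State whether odd cycles started after permanent discontinuation of NT-I7 count.
- **Pembrolizumab:** keep the current formula.

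If relative dose intensity is added, use the dose planned at each scheduled administration as the reference, not the dose at Cycle 1 Day 1. In the Biomarker Cohort the plan allows 960 to rise to 1200 µg/kg at Cycle 5. Two doses at each level average (960 + 960 + 1200 + 1200)/4 = 1080, which is 1080/960 = 112.5% of the starting dose although every dose was as planned. Against the planned doses it is 100%.

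The cost is one SAP line and a small programming change, using dosing data already collected. For a fully dosed subject the new row will equal the existing dose per administration; it adds information only when doses are omitted. Dropping the row for NT-I7 would also remove the artefact, but would leave no NT-I7 dose-per-interval measure that explicitly counts omitted doses.
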